#### **4.1.1 Run-In Period**

During this two-week period, all participants will send a photo of their medicine or catheter in hand at time of treatment to the WTH phone number provided at enrollment. Participants will receive \$20 (to be administered via Greenfire Clin Card), regardless of their adherence score, given in a lump sum at the end of the run-in period.

---

---

## **4.2 Study Treatment for Arm 1**

### **4.2.1 Intervention Phase**

Participants will receive daily text messages as reminders and continue to report real-time treatment adherence with photos. They will receive \$2/week to encourage real-time adherence reporting. Pay is not contingent on meeting a target adherence score, but only on submitting at least one photo at time of treatment per week. In addition, participants will be able to log in to WTH to see their personal dashboard with a visual display of their weekly adherence performance and educational materials relevant to their disease group. Parents/legal guardians will have access to these same educational materials via their own WTH portals. Additionally, to mitigate the minimal risk of this study, parents/legal guardians will be notified if their child is excessively non-adherent. This portion of the study will last for 6 months. At the end of this phase, participants and parents/legal guardians will be asked to answer the baseline questionnaires again. Participants who complete their surveys within 5 days will receive \$20. Participants who complete their surveys within 6 – 10 days will receive \$10.

### **4.2.2 Follow-Up Phase**

After 6 months, participants will receive a message that the main study intervention is ending. At this time, participants and parents/legal guardians, if applicable, will be prompted to complete the baseline questionnaires again. Arm 1 will continue to receive reminders and report their daily adherence with mobile phone camera photography and earn \$2/week for reporting. Parents/legal guardians will continue to be notified if their child is excessively non-adherent. Parents/legal guardians and participants will no longer have access to their WTH portal during this period. This portion of the study will last for 6 months. At study completion, participants and parents/legal guardians will be asked one final time to answer the baseline questionnaires. Participants who complete their surveys within 5 days will receive \$20. Participants who complete their surveys within 6 – 10 days will receive \$10.

## **4.3 Study Treatment for Arm 2**

### **4.3.1 Intervention Phase**

Participants randomized to Arm 2 will also begin to receive daily text messages as reminders and report real-time treatment adherence with photos, and will have web access to the educational modules through the WTH portal. In contrast to Arm 1, they will receive their weekly performance results by text to their phone with tailored feedback. In Arm 2, participants will receive \$10 per week for adherence reporting during this 6-month intervention phase if they perform their desired treatment behavior at least 85% of the time. Incentive notification will be texted to participants based on their adherence behavior. Parents/legal guardians will have access to these same educational materials via their own WTH portals. Additionally, to mitigate the minimal risk of this study, parents/legal guardians will be notified if their child is excessively non-adherent. This portion of the study will last for 6 months. At the end of this phase, participants and parents/legal guardians will be asked to answer the baseline questionnaires again. Participants who complete their surveys within 5 days will receive \$20. Participants who complete their surveys within 6 – 10 days will receive \$10.

---

---

### **4.3.2 Follow-Up Phase**

After 6 months, participants will receive a message that the main study intervention is ending. At this time, participants and parents/legal guardians will be prompted to complete the baseline questionnaires again. Arm 2 will be told that incentives will be tapered. Parents/legal guardians and participants will no longer be able to access the WTH Portal. Arm 2 participants will get \$2 per week for reporting during this follow-up period and will continue to receive weekly adherence feedback texted to them. Parents/legal guardians will continue to be notified if their child is excessively non-adherent. They will be eligible to receive an additional \$10 for meeting their adherence target of  $\geq 85\%$  over a 2 week period x 4 (as opposed to one week during the intervention period). The incentive will then become \$10 every month for two months (if the average monthly goal is met), and finally no incentive beyond the \$2 per week for reporting. This portion of the study will last for 6 months. At study completion, participants and parents/legal guardians will be asked one final time to answer the baseline questionnaires. Participants who complete their surveys within 5 days will receive \$20. Participants who complete their surveys within 6 – 10 days will receive \$10.

### **4.4 Study Staff Check-Ins**

Study staff will phone participants at the time of randomization, at the end of six months and end of follow-up period to answer any questions. Study staff will also contact participants if they fail to report adherence for more than 3 days in a row to assess barriers, such as technical issues, etc.

### **4.5 Subject Completion/Withdrawal**

Study subjects may withdraw from the study at any time for any reason without prejudice to their care. If a participant who has been randomized chooses to withdraw, a study member will send them a link to the Exit Survey. If the participant completes the Exit Survey within five days of receiving the link, the participant will be paid \$10 as a thank you for their time.

## **5 STUDY EVALUATIONS AND MEASUREMENTS**

### **5.1 Screening and Monitoring Evaluations and Measurements**

#### **5.1.1 Medical Record Review**

- Date of birth
  - Weight and height
  - Demographic data including age, race, gender, education level, insurance status, household income, possession of a 504/IEP plan, languages spoken at home, living arrangement and accessibility to care
  - Medical history, including reason for transplant, time since transplant, etiology of renal or hepatic disease, age at initial diagnosis, history and length of preceding dialysis, baseline GFR, transplant complications, and delayed graft function
  - Chart review in EPIC will be updated every 6 months from study entry for each
-

---

subject. For kidney transplant recipients, chart review will include immunosuppressive drug levels, hospitalization events, rejection episodes, graft failure events, biopsies and serum creatinine, number of medications, number of pills and other clinically relevant data. For spina bifida subjects, chart review will include level of lesion, type of spina bifida, number of shunt surgeries, ambulation method, other co-morbidities, baseline bladder capacity and compliance, route of catheterization, history of urinary tract infection, number of medications, frequency of catheterization and other clinically relevant data.

- No biopsies or any other medical procedures beyond standard of care will be done solely for this study. Study staff will review clinical biopsy results when chart reviews are completed.

## **5.2 Efficacy Evaluations**

### **5.2.1 Diagnostic Tests, Scales, Measures, etc.**

All surveys will be administered and entered directly by and into the WTH portal. The KT and SB subjects will complete the same baseline executive function measure, perceived adherence barriers, and self-efficacy scale. Since few other forms have been validated in both disease groups, KT and SB participants will complete different forms measuring healthcare responsibility & disease knowledge. The forms parents/legal guardians will complete are indicated below. Surveys will be completed at enrollment, end of intervention and study completion.

Both KT and SB subjects will complete:

- Behavior Rating Inventory of Executive Function – Adult (BRIEF-A) for participants over 18 & parents will complete BRIEF2-Parent (BRIEF-P) if the subject is <18 years of age
- Adolescent Medication Barrier Scale (AMBS) & parents will complete Parent Medication Barrier Scale (PMBS)
- Self-Efficacy for Managing Chronic Disease 6-Item Scale
- Way to Health Exit Survey – to be completed at withdrawal or study completion

Only KT subjects will complete:

- Allocation of Treatment Responsibility (ATR) & parents will complete the Allocation of Treatment Responsibility – Caregiver (ATR-C)
- Heart Transplant Knowledge questionnaire (adapted for KT)

Only SB subjects will complete:

- Sharing of Spina Bifida Management Responsibilities - Child (SOSBMR-C) parents
-

will complete the Sharing of Spina Bifida Management Responsibilities – Parent (SOSBMR-P)

- Knowledge of Spina Bifida (KOSB)
- SB Barriers and Cathing Barriers Measure

Item Measured	Forms for KT Group	Forms for SB Group
Executive Function	BRIEF-Adult; BRIEF2-Parent	BRIEF-Adult; BRIEF2-Parent
Perceived Adherence Barriers	AMBS/PMBS	SB Barriers and Cathing Barriers Measure
Self-Efficacy	Self-Efficacy For Managing Chronic Disease 6-item Scale	Self-Efficacy For Managing Chronic Disease 6-item Scale
Treatment Responsibility	ATR; ATR-Caregiver	SOSBMR-Child; SOSBMR-Parent
Knowledge of Condition Assessment	Heart Transplant Knowledge Questionnaire (adapted for KT)	KOSB
Efficacy of Way to Health Portal	Way to Health Exit Survey; Way to Health Exit Survey - Parent	Way to Health Exit Survey; Way to Health Exit Survey - Parent

### 5.2.2 Survey Descriptions

- Adolescent/Parent Medication Barriers Scale (AMBS and PMBS) is a 17-item scale that examines perceived barriers to medication adherence, in 3 categories: Disease Frustration/Adolescent Issues, Ingestion Issues, and Regimen Adaptation/Cognitive Issues. AYA answer questions on a Likert scale, from “strongly disagree” to “strongly agree,” with higher scores representing a greater amount of perceived barriers to treatment. For KT subjects < 18 years of age, parents will complete a parallel parent-specific survey (PMBS). The PMBS measures the same 3 factors, plus a Parent Reminder item. Results of these surveys will be recorded in the WTH study database.
- Allocation of Treatment Responsibility (ATR and ATR-Caregiver): all participants will complete the ATR; their parents will complete the ATR-Caregiver. The ATR questionnaire helps to identify who is responsible for the medication taking routine and how those responsibilities are divided between the subject and their parent/caregiver(s). The ATR is a 3 part questionnaire: Part 1: General Information on treatment responsibility, Part 2: Report of adolescent subject’s treatment

---

responsibility, Part 3: Report of parent/ caregiver's treatment responsibility. The ATR-Caregiver has the same 3 parts.

- Behavior Rating Inventory of Executive Function (BRIEF) is a validated measure designed to assess executive function in daily life. The *BRIEF2-P (Parent version)* is a 63-item validated measure that documents the parent's perception of their child's problem-solving and behavioral functioning. This form will be administered to parents of participants under 18 years of age. The *BRIEF-A (Adult version)* is a 75-item validated, self-report measure for participants 18 or older. Both study forms take approximately 10-15 minutes to complete and measure different aspects of executive function, such as inhibition, self-monitoring, organization, planning, and emotional control. The BRIEF is scored against population normative data and reported as an overall summary score with subscales and two broad indexes (behavioral regulation and metacognition). Both versions of the BRIEF have high reliability, validity and clinical utility across diverse disease populations and age groups.
  - Heart Transplant Knowledge Questionnaire (adapted for KT) is a 20-question survey used to assess the participants understanding of their medication, transplant and healthcare plan. The survey resembles a quiz, with each multiple choice and true/false question having only one correct answer.
  - Knowledge of Spina Bifida (KOSB) is an 18-item survey assessed as a summary score. Higher scores indicate greater knowledge.
  - Self-Efficacy for Managing Chronic Disease 6-Item Scale is a Likert-scale survey that measures the following six domains of self-efficacy: (1) fatigue, (2) physical discomfort, (3) emotional distress, (4) symptoms or health problems, (5) health-related self-management tasks and (6) taking medicines. Each item is answered on a 10-point Likert scale, with higher scores representing greater healthcare self-efficacy.
  - Sharing of Spina Bifida Management Responsibilities – Child and – Parent (SOSBMR-C and -P) measure perceived responsibility for health-related tasks, asking who took responsibility, child, parent or equal, for 34 health-related tasks pertaining to SB.
  - Spina Bifida Barriers and Cathing Barriers Measures are two barriers measures combined into one survey for ease of administration. The first, SB Barriers, was used in a prior study by [name], a member of the DCC study staff. This measure was adapted from a validated diabetes barriers scale and asks subjects about their perceived barriers to proper care. The Cathing Barriers Measure is not formally validated but showed content validity in a recent study. The survey asks subjects to indicate the items that make cathing difficult and then to rank the top three items out of those indicated. To our knowledge, there are no validated measures that address perceived barriers to cathing for the SB population.
  - Way to Health Exit Survey measures the efficacy of the Way to Health portal as a tool for the research and engagement of AYA with a kidney transplant of spina bifida in
-

---

their health care management. This measure was developed by the study research team; it asks about the participants' attitude towards the portal, the study and asks about the effectiveness of the portal.

## 6 STATISTICAL CONSIDERATIONS

### 6.1 Primary Endpoint

The primary endpoint for this pilot clinical trial is to compare the efficacy of two 6-month mhealth-based interventions to promote treatment adherence among AYA with KT or SB.

The **independent variable** in the analyses for Aim 1 is *exposure to feedback + incentive* (intervention, Arm 2). The **dependent variable**, or primary outcome measure, is: change in the *proportion of weeks with adherence behavior  $\geq 85\%$  expected between baseline (run-in period) and intervention period*. Weekly adherence proportions will be calculated by observing the number of non-missed/late treatment episodes over the total number of episodes in that week.

The outcome will then be the proportion of weeks with treatment adherence  $\geq 85\%$ . Participants who do not submit the correct number of pictures within the prescribed window of their expected time due for treatment will be counted as nonadherent for that episode of med taking/cathing. Over the study period, changes in weekly timing adherence will be assessed as a repeated measure over time. In secondary analysis, we will examine variability in inter-dose intervals (based on time-stamping of photos) to account for doses that are taken beyond the time window.

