### **2.1 Primary Objective**

The primary objective is to compare the efficacy of two 6-month mhealth-based interventions to promote treatment adherence among AYA with KT or SB. In Arm 1, subjects will receive text reminders and a nominal weekly payment for participation. Arm 2 is an enhanced, tailored intervention with individualized feedback on adherence behavior and financial incentives for meeting adherence goals. The primary outcome is change in proportion of time adherent between run-in and 6-month intervention. Adherence data will be collected in real-time when subjects take pictures of their medicines (or catheter) in hand. Secondary outcomes are coefficient of variation (CV) in immunosuppressive drug levels for KT recipients and change in bladder wall compliance for SB subjects. Hypothesis 1: Adherence will be higher during the 6-month intervention in Arm 2 vs. Arm 1.

---

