**Arm 1:** Participants will begin to receive daily text messages as reminders and continue to report real-time treatment adherence with photos. They will receive \$2/week to encourage real-time adherence reporting. Pay is not contingent on meeting a target adherence score, but only on submitting at least one photo per week. In addition to the payments, participants will be able to log in to WTH to see their personal dashboard with a visual display of their weekly adherence performance. They will also be able to access educational resources related to their primary disease. Educational materials for KT recipients will include web links to participant resources specific for AYA, including resources publicly available through the American Society of Transplantation, National Kidney Foundation and the United Network for Organ Sharing and educational videos created by CHOP's care team. The major transplant themes that will be covered include: medication management, infection precautions, energy and physical activity, mental health and social adjustment, nutrition, sexuality and risk behavior education, and vocational resources. Similarly, educational materials for the SB subjects will be drawn from web-based AYA-specific resources, including web links to the Centers for Disease Control Living with Spina Bifida Program and the National Spina Bifida Association. The major SB themes that will be covered include: bladder and bowel management, infection precautions, skin health, physical health, mental health and social adjustment, nutrition, sexuality and risk behavior, safety and vocational resources. All of the educational materials that will be used have been vetted by healthcare professionals, but every resource will be reviewed and adapted by the investigative team to ensure relevance, currency, accuracy and readability. Every month, participants will receive a text encouraging them to visit the WTH educational modules and to check their earnings. WTH is able to track usage of the modules by individual. Parents/legal guardians will have access to these same educational materials via their own WTH portals. Additionally, to mitigate the minimal risk of this study, parents/legal guardians will be notified if their child is excessively non-adherent.

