**Arm 2:** Participants randomized to Arm 2 will also begin to receive daily text messages as reminders and report real-time treatment adherence with photos, and will have web access to the educational modules through the WTH portal. Similarly, every month, participants will receive a text encouraging them to visit the WTH educational modules and to check their earnings. In contrast to Arm 1, they will receive their weekly performance results by text to their phone with tailored feedback, e.g. "Congratulations. You performed your cathing every time you needed to this week. Cathing regularly helps you prevent infections and keeps your kidneys healthy. Keep up the strong work!" or "You took your medicines on time 3 out of 4 times this week. Taking medicines can be hard. Check out the WTH link on tips for improving your timing (with URL inserted). Hang in there!" In Arm 2, participants will not receive \$2/week for adherence reporting during this 6-month intervention phase. Instead, they will receive a larger incentive of \$10/week if they perform their desired treatment behavior at least 85% of the time. Incentive notification will be texted to participants: "Congratulations. You earned \$10 for your hard work being consistent with cathing/taking your medicine. Way to take care of yourself!" or "You just missed earning \$10 this week. You were really close. If

---

---

you remember just two more times next week, your hard work will pay off with \$10 in your pocket and better health.”

Text messages will be gain-framed, i.e. will focus on what the participant has accomplished vs. what he/she has not. The text message bank for U-REACT will be adapted from [name] prior texting intervention with AYA cancer survivors (THRIVE: Texting Health Resources to Inform, Motivate and Engage) which has an established repository of over 120 positively-framed motivational health messages.

Similarly to Arm 1, parents/legal guardians will have access to the same educational materials via their own WTH portals. Additionally, to mitigate the minimal risk of this study, parents/legal guardians will be notified if their child is excessively non-adherent.

At the end of the intervention phase, participants and parents/legal guardians, again, will complete the baseline questionnaires. Participants who complete their surveys within 5 days will receive \$20. Participants who complete their surveys within 6 – 10 days will receive \$10.

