### **3.1.3 Follow-up Phase**

Six months after randomization, participants will receive a message that the main study intervention is ending but that we will continue to track their adherence reporting to understand the benefits of the study. At this time, all participants and parents/legal guardians will repeat the baseline questionnaires. Arm 1 will continue to receive reminders and report their daily adherence with mobile phone camera photography and earn \$2/week for reporting, but they will no longer have access to their WTH portal, i.e. no visualization of dashboard or educational modules. Arm 2 will be told that incentives will be tapered. They will no longer be able to access the WTH portal. Arm 2 participants will get \$2/week for reporting during this follow-up period and will continue to receive weekly adherence feedback texted to them. They will be eligible to receive an additional \$10 for meeting their adherence target of  $\geq 85\%$  over a lengthened time interval. Specifically, they will receive feedback and \$10 every 2 weeks x 4 (if goal is met over average of preceding 2 weeks), then \$10 every month x 2 (if average monthly goal is met) then no incentive (beyond the \$2/week for reporting) for the last two months. At the end of the follow-up phase, participants and parents/legal guardians, again, will complete the baseline questionnaires. Participants who complete their surveys within 5 days will receive \$20. Participants who complete their surveys within 6 – 10 days will receive \$10.

Parents/legal guardians will no longer have access to their WTH portal during this phase, but will still receive messages if their child is excessively non-adherent.

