#### 6.5 Statistical Methods

Clinical and demographic variables will be compared with chi-square or two-sample t-tests for parametric and Fisher's exact or Wilcoxon rank-sum tests for non-parametric data. Treatment groups will be compared with similar analyses to confirm equity in randomization. We will compare change over time in % adherence between arms by fitting quasi-least squares (QLS) and generalized estimating equation (GEE) longitudinal models. The QLS/GEE models include a regression model for the primary outcome variable, in addition to a separate model for the correlation amongst the repeated measures on each subject. The AR (1) correlation structure is plausible because it forces a decline between measures with increasing separation in time; however, we will assess the sensitivity of results to choice of structure. In addition, the models will include treatment group and a time by treatment group interaction. If the interaction term differs significantly from zero, this will indicate that the change over time differs significantly between treatment groups. All analyses will follow the intention-to-treat principle. We will analyze the results for each disease group (SB, KT) separately, although the overall analytical models are the same.

Analysis for Aim 1 and Aim 2 will utilize GEE/QLS models to compare the change over time in the outcome between arms.

For Aim 3, Pearson's or Spearman's Correlations will be calculated to observe the association between outcome and each independent variable.

The statistical analysis will follow the intention-to-treat principle.

---

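### The plan does not settle whether weeks at or above 85% or percentage adherence is the primary scale; the 85% weekly cut is also the one paid for in Arm 2 only, and the stated power is not for it

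*Combined protocol and SAP*

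**What the plan says.** **Primary outcome.** Section 6.1 first forms a percentage for each week: "Weekly adherence proportions will be calculated by observing the number of non-missed/late treatment episodes over the total number of episodes in that week". A treatment without a timely photo "will be counted as nonadherent for that episode of med taking/cathing". The week is then reduced to yes or no: "The outcome will then be the proportion of weeks with treatment adherence" at or above 85%. Section 6.3 uses the same 85% definition as the dependent variable for Aim 3.

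**Other descriptions of the outcome.** Section 2.1 says: "The primary outcome is change in proportion of time adherent between run-in and 6-month intervention". Section 6.5 says: "We will compare change over time in % adherence between arms", using QLS and GEE models. It sends Aims 1 and 2 through those models without defining a separate Aim 2 outcome. Section 6.6 bases power on a difference of 8 points in average improvement in timing adherence, with SD 16.

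**Payment.** In the intervention phase (section 3.1.2; also 4.3.1 and 8.7), Arm 2 earns 10 dollars a week "if they perform their desired treatment behavior at least 85% of the time". Arm 1 earns 2 dollars a week: "Pay is not contingent on meeting a target adherence score, but only on submitting at least one photo per week". In follow-up (section 3.1.3), Arm 2's extra payment is first made "if goal is met over average of preceding 2 weeks", then on a monthly average, and then stops.

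**The concern.** There are two linked problems. First, sections 6.1, 6.5 and 6.6 do not describe one outcome. A share of weeks above a cut and a mean percentage are different quantities with different variances, and can give different answers on the same photos. The plan does not say which is decisive.

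Second, the cut in section 6.1 is not neutral between the arms. It is the event, in the window, for which one arm is paid. Effort in Arm 2 may therefore gather around the cut in a way that it has no financial reason to do in Arm 1. The outcome gives full credit for a week that just crosses 85% and none for any change that stays on one side.

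The trial asks whether treatment adherence improves. A between-arm difference in weeks at or above 85% could overstate the change in overall adherence, and a reader given only that measure could not tell.

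**Working it through.** **1. The plan's own power figure (section 6.6).** Inputs: difference 8, SD 16, 90 per arm, alpha 0.05 (two-sided assumed, as sidedness is not stated for this test).

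Effect size = 8/16 = 0.50. Normal approximation: power = Φ(0.50 × √(90/2) − 1.96) = Φ(3.354 − 1.960) = 0.918. The noncentral t gives 0.916. The stated figure of more than 90% reproduces; 85 per arm would give 90%.

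**2. What that figure covers.** Its inputs are most naturally read as mean timing adherence in percentage points. The plan gives no SD for the change in the share of weeks at or above 85%, and 16 cannot be assumed for it. The run-in lasts two weeks, so each baseline share can only be 0, 0.5 or 1. For a participant with an even chance of reaching the cut in each week, and independent weeks (both assumed), the baseline share alone has SD √(0.5 × 0.5/2) = 0.35.

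A simulation shows the possible range. Its assumptions are a logit-normal model with person SD 1.0, week SD 0.5 and person-level change SD 0.8, 14 episodes a week, 2 run-in and 26 intervention weeks, a true mean gain of 8 points, and 90 per arm.

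| Baseline mean | Mean adherence: SD of change, power | Weeks ≥85%: gain, SD of change, power |
|---|---|---|
| 65.5% | 17.6, 86% | 12.4, 34.8, 66% |
| 75.5% | 15.4, 94% | 15.5, 36.9, 80% |
| 83.7% | 12.7, 99% | 17.8, 35.1, 92% |

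**3. The cut in episodes.** Once-daily regimens are excluded (section 3.4.2), so at least 14 episodes a week are assumed. 0.85 × 14 = 11.9, so 12 of 14 (85.7%) passes and 11 of 14 (78.6%) fails.

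**4. Same mean, different outcome.** Every week at 11/14: mean 78.6%, 0% of weeks pass. Three weeks at 12/14 and one at 8/14: (36 + 8)/56 = 78.6%, 75% of weeks pass.

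**5. A small shift across the cut (assumed mix).** Arm 1 has 40% of weeks at 13/14, 30% at 11/14 and 30% at 8/14. Mean = 0.4 × 13/14 + 0.3 × 11/14 + 0.3 × 8/14 = 77.9%, and 40% of weeks pass. If Arm 2 differs only in turning 11/14 into 12/14, its mean is 80.0% and 70% of weeks pass: 2.1 points against 30.

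**6. Direction.** With mean adherence held equal and 14 episodes a week, raising the assumed within-week correlation from 0 to 0.2 (more week-to-week spread) moves the share of passing weeks from 45% to 57% at a mean of 80%, but from 84% to 79% at a mean of 90%. The sign is not fixed.

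**7. Follow-up, Aim 2 only.** Weeks of 14/14 and 10/14 give 24/28 = 85.7%: paid on the two-week average, but only 1 of 2 weeks passes. Weeks of 14, 14, 10 and 10 give 48/56 = 85.7%: paid over four weeks, with 2 of 4 passing. This matters only if Aim 2 is scored on the weekly cut.

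**The case against.** The strongest reply is that paying for a target and measuring whether it is reached is an open and coherent design choice. Arm 2's intervention is the incentive, and crossing the cut is a real gain: in step 5 mean adherence does rise. The plan is also not limited to the cut. Section 6.1 adds weekly timing adherence as a repeated measure and a secondary analysis of inter-dose intervals. Section 6.5 models percentage adherence. Section 6.2 has drug-level variability and bladder compliance, neither tied to payment. A gain confined to the cut would probably show there. All of this stands, and it makes the shared cut a risk of interpretation rather than a contradiction. It does not answer which scale is decisive, or give the continuous measure a stated supporting role.

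A reader might infer four stronger things that the documents do not support:

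- *That the widening payment window in follow-up moves the primary endpoint.* It cannot: the primary outcome ends with the intervention (sections 2.1 and 6.1). What widens is the payment window, not the scoring week. It bears on Aim 2 only, and only if Aim 2 uses the 85% cut, which section 6.5 leaves open. Section 2.2 also looks to six months after the intervention, and no extra payment operates in the last two months.
- *That Arm 2 will give up once a week is lost, so true adherence falls.* The plan describes no such behaviour. Both arms have daily reminders, staff contact after more than 3 silent days and parent notification, and Arm 2's feedback is graded.
- *That the bias must favour Arm 2.* Step 6 shows that the direction can reverse.
- *That the trial is underpowered on the section 6.1 outcome.* The simulated range of 66% to 92% rests on assumptions. The documents show only that no power is stated for that outcome.

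The wording of section 2.1 does not settle the scale either: it could be shorthand for the share of adherent weeks.

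**Conclusion.** The point holds as a mismatch between sections 6.1, 6.5 and 6.6, made more important because the section 6.1 cut is paid for in one arm only. Two parts rest on the documents alone: the decisive scale is not fixed, and the reproduced 91.8% power belongs to a mean change in timing adherence rather than to the share of weeks at or above 85%.

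The possible size of a divergence rests on assumptions. Under the mix in step 5, the section 6.1 outcome differs by 30 points when mean adherence differs by 2.1. Other patterns give smaller gaps or the opposite sign. The conclusion is that a difference on the 85% measure could overstate the change in overall adherence, not that it will. The matter should be settled before outcomes are compared between arms.

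**What to change.** In section 6.1, make the continuous weekly percentage of on-time episodes the primary measure, which agrees with sections 6.5 and 6.6. Name the same measure as the Aim 2 outcome. Keep the proportion of weeks at or above 85% as a secondary, goal-attainment outcome, and align the Aim 3 wording in section 6.3 with whichever measure is chosen.

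If the sponsor prefers to keep the 85% cut as primary, label the continuous percentage as the prespecified supporting analysis for Aims 1 and 2, report both estimates with confidence intervals, and restate the power for the 85% outcome with a stated SD and its source. No added rule that the two measures must agree is needed.

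The cost is small. The photos already collected give both measures, and on the plan's own inputs the continuous primary needs no change in sample size. The downside is that goal attainment becomes secondary or, under the alternative, that one more prespecified analysis is reported and the power must be recalculated.
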